3.3.2 Exclusion Criteria

1. Known hypersensitivity or contraindication to any component of study treatment or their excipients.
2. Previous Grade 3-4 AEs, or discontinuation of PD-1 or CTLA-4 inhibitor therapy, or BRAF/MEK inhibitor therapy
3. Inability to swallow and retain study treatment

4. Impairment of gastrointestinal function or disease which may significantly alter the absorption of study treatment (e.g., active ulcerative disease; uncontrolled nausea, vomiting or diarrhea; malabsorption syndrome; small bowel resection).
5. Participants with a non-melanoma related condition requiring systemic treatment with either corticosteroids (> 10 mg daily prednisone equivalents) or other immunosuppressive medications within 14 days of study drug administration. Inhaled or topical steroids, and adrenal replacement doses > 10 mg daily prednisone equivalents are permitted in the absence of active autoimmune disease.
6. Participants with active, known or suspected autoimmune disease including those who have required systemic anti-rheumatic therapies in the preceding 2 years. Participants with vitiligo, type I diabetes mellitus, residual hypothyroidism due to autoimmune condition only requiring hormone replacement, psoriasis not requiring systemic treatment, or conditions not expected to recur in the absence of an external trigger are permitted to enroll.
7. Impaired cardiovascular function or clinically significant cardiovascular disease including, but not limited to, the following:
 - a. History of acute coronary syndromes (including myocardial infarction, unstable angina, coronary artery bypass grafting, coronary angioplasty or stenting) < 6 months prior to Screening
 - b. Congestive heart failure requiring treatment (New York Heart Association Grade ≥ 2)
 - c. A known LVEF $< 50\%$ as determined by MUGA or ECHO
 - d. Uncontrolled hypertension defined as persistent systolic blood pressure ≥ 150 mmHg or diastolic blood pressure ≥ 100 mmHg despite current therapy
 - e. History or presence of clinically significant cardiac arrhythmias (including resting bradycardia, uncontrolled atrial fibrillation or uncontrolled paroxysmal supraventricular tachycardia)
 - f. Baseline QTcF interval ≥ 480 ms.
8. Second malignancy that requires active treatment or would interfere with treatment efficacy evaluation. Participants with a second malignancy treated with curative intent are eligible.
9. On-going or use of systemic antibiotics during the preceding 2 weeks prior to enrollment
10. Known acute or chronic infection with hepatitis B or hepatitis C virus. Participants treated with curative anti-viral therapy are eligible.

11. Known history of testing positive for human immunodeficiency virus (HIV) or known acquired immunodeficiency syndrome (AIDS) even if fully immunocompetent on ART—due to the unknown effects of HIV on the immune response to combined nivolumab plus ipilimumab or the unique toxicity spectrum of these drugs in patients with HIV.
12. Clinically unstable thromboembolic event despite anti-coagulation. Patients on stable dosing of anti-coagulants per investigator discretion are eligible.
13. Use of herbal supplements, medications or foods that are moderate or strong inhibitors or inducers of cytochrome P450 (CYP) 3A4/5 ≤ 1 week prior to the start of study treatment (Section 4.5.1).
14. History or current evidence of retinal vein occlusion (RVO) or current risk factors for RVO (e.g., uncontrolled glaucoma or ocular hypertension, history of hyperviscosity or hypercoagulability syndromes); history of retinal degenerative disease.

3.3.3 *Phase II Group 1 Specific Criteria*

1. For Phase II Group 1 (Brain Metastases): Patients may have an ECOG status of 0–2 and IS permitted to be on corticosteroids if related to disease burden and MAY have symptomatic brain lesions as long as radiation or surgical intervention is not deemed to be urgently necessary.
 - a. Symptomatic intracranial metastases may be on steroids at a total daily dose of no higher than 4 mg of dexamethasone or equivalent that is stable or tapering for 10 days prior to first treatment,
 - b. have no immediate need for SRT or surgery (within 3 week prior to first treatment),
 - c. have had no experience of seizure within 10 days prior to first treatment.

3.3.4 *Women of Childbearing Potential*

A Women of childbearing potential (WOCBP) is defined as any female who has experienced menarche and who has not undergone surgical sterilization (hysterectomy or bilateral oophorectomy) and is not postmenopausal. Menopause is defined as 12 months of amenorrhea in a woman over age 45 years in the absence of other biological or physiological causes. In addition, females under the age of 55 years must have a serum follicle stimulating hormone, (FSH) level > 40 mIU/mL to confirm menopause.

*Females treated with hormone replacement therapy, (HRT) are likely to have artificially suppressed FSH levels and may require a washout period in order to obtain a physiologic FSH level. The duration of the washout period is a function of the type of HRT used. The duration of the washout period below are suggested guidelines and the investigators should use their judgment in checking serum FSH levels. If the serum FSH level is >40

mlU/ml at any time during the washout period, the woman can be considered postmenopausal:

- 1 week minimum for vaginal hormonal products (rings, creams, gels)
- 4 weeks minimum for transdermal products
- 8 weeks minimum for oral products. Other parenteral products may require washout periods as long as 6 months.

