- To evaluate the overall survival (OS) of triple or quadruple therapy in high-risk population of *BRAF*-mutated, metastatic melanoma

Study Design

This is an open label, multi-site, phase 1/2 study of encorafenib +/- binimetinib + nivolumab + ipilimumab for the treatment of patients with unresectable or metastatic *BRAF*-mutated melanoma in high risk cohorts.

Study participants will consist of metastatic melanoma patients harboring *BRAF*^{V600E/K} mutation without previous frontline therapy or recently started treatment with up to 6 weeks of targeted therapy, or one cycle of immunotherapy (or > 6 months from adjuvant therapy). Toxicity from prior treatment must have resolved to ≤ Grade 1 and not included previous Grade 3–4 immune-related adverse events (irAEs) that required treatment discontinuation or previous Grade 2 immune-related uveitis or pneumonitis.

Phase I, Cohort 1: Twelve patients will be treated with 300mg encorafenib and 3mg/kg nivolumab and 1 mg/kg ipilimumab. The dose limiting toxicity (DLT) for cohort 1 will be evaluated between weeks 1–6.

[figure not shown]
Phase I, Cohort 2: Upfront quadruple therapy with 450mg encorafenib, 45mg binimetinib, 3mg/kg nivolumab and 1mg/kg ipilimumab will be investigated with 12 participants. DLT window for phase I, cohort 2 will be evaluated at weeks 1–6.

Upon establishment of RP2R schedule, only participants with advanced melanoma who are treatment naïve in metastatic setting or have had up to 6 weeks of targeted therapy, or one cycle of immunotherapy, or who have progressed on adjuvant therapy for more than 6 months following completion of adjuvant therapy (either *BRAF*-MEK or PD1 Ab) will be eligible for participation in high risk disease cohort expansion (Groups 1 or 2).

Phase I/II study of encorafenib with and without binimetinib with nivolumab and low dose ipilimumab in metastatic *BRAF* mutant melanoma

Phase II will employ the RP2R schedule from Phase I and investigate the early efficacy in participants with high risk features who are less likely to derive benefit from standard treatment approaches and who may benefit from quadruple therapy despite the potential for increased toxicity. These will include: Group 1) symptomatic brain metastases [up to 30 patients] and Group 2) Elevated LDH >1x upper limit of normal (ULN) with: a) liver metastases OR b) bulky visceral disease (sum of longest diameter (SLD) > 44mm) [combined with Group 1 up to 60 total patients].

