3. INVESTIGATIONAL PLAN

3.1 Study Design and Duration

This is an open label, multi-site, phase 1/2 study of encorafenib +/- binimatinib + nivolumab + ipilimumab for the treatment of participants with unresectable or metastatic *BRAF*-mutated melanoma in high risk cohorts.

Study participants will consist of metastatic melanoma patients harboring *BRAFV600E/K* mutation without previous frontline therapy or recently started treatment with up to 6 weeks of targeted therapy, or one cycle of immunotherapy (or >6 months from adjuvant therapy). Toxicity from prior treatment must have resolved to ≤ Grade 1 and not included previous Grade 3–4 irAEs that required treatment discontinuous or previous Grade 2 immune-related uveitis or pneumonitis.

Phase I, Cohort 1: Twelve patients will be treated with triple therapy: 300 mg encorafenib and 3mg/kg nivolumab and 1 mg/kg ipilimumab. Dose-limiting toxicity (DLT) for Cohort 1 will be evaluated at week 6.

[figure not shown]
Phase I, Cohort 2: Upfront quadruple therapy (450mg encorafenib, 45mg binimatinib, 3mg/kg nivolumab, and 1mg/kg ipilimumab) will be investigated with twelve patients. DLT for Phase I, Cohort 2 will be evaluated at week 6.

Prior studies with triplet therapies combining anti PD-1/PD-L1, *BRAF*, and MEK inhibition have shown Grade 3–4 AEs occurring from 58%–73%^{5,43,44,68}. These initial cohorts were small and did not use the newer, more potent and specific *BRAF*/MEK inhibitor pair encorafenib/binimatinib. We are allowing an initial DLT rate up to 75% in a continuous Bayesian monitoring protocol (See Statistics Section 8). We anticipate most of the toxicities to be additive and not synergistic and based on earlier recognition and treatment of immunotherapy AEs (see Appendix 6) and very specific AEs from encorafenib and binimatinib (see Appendix 2 and 3), we anticipate being able to create a safe RP2R dosing schedule.

Upon establishment of RP2R schedule, only participants with advanced melanoma who are either treatment naïve in the metastatic setting, have recently started treatment with targeted therapy within the past 6 weeks, or one cycle of immunotherapy, or who have progressed on adjuvant therapy more than 6 months following completion of adjuvant therapy (either *BRAF*-MEK or PD1 Ab) will be eligible for participation in high risk disease cohort expansion (Groups 1 or 2, see Schema below).

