3.3 Study Population

For entry into the study, the following criteria MUST be met.

3.3.1 *Inclusion Criteria*

1. Signed Written Informed Consent
 - a. Participants must have signed and dated an IRB/IEC approved written informed consent form in accordance with regulatory and institutional guidelines. This must be obtained before the performance of any protocol-related procedures that are not part of normal subject care.
 - b. Participants must be willing and able to comply with scheduled visits, treatment schedule, laboratory testing, and other requirements of the study.
2. Age ≥ 18 years
3. Histologically confirmed diagnosis of unresectable or metastatic melanoma
4. Presence of *BRAFV600E/K* mutation in tumor tissue as determined in a CLIA certified laboratory
5. Patients are required to submit archival biopsy material, if available, and submit research blood samples prior to first dose. Ten patients in each Phase I cohort will undergo fresh biopsy. These will be the first 10 unless medical or societal factors (e.g. COVID19) limit the pursuit of research biopsies.
6. Patients must be greater than 6 months from completion of adjuvant therapy (if any given) and/or treatment naïve in the metastatic setting or have recently started targeted therapy within the last 6 weeks, or one cycle of immunotherapy.
7. Prior radiotherapy must have been completed at least 2 weeks prior to study drug administration.
8. An ECOG Performance Status of 0 or 1. If enrolling in Group 1 of Phase II, can have Performance Status from 0-2.
9. Measurable disease by CT or MRI per RANO-BM (brain metastases) OR RECIST v1.1 criteria
10. Must have high risk features described as described in Phase II expansion cohort – EITHER brain metastases as described in Phase II Group 1 OR Elevated LDH/Bulky Visceral Disease as described in Phase II Group 2.

11. Adequate bone marrow, organ function, and laboratory parameters:

- a. ANC > 1.5×10^9 /L;
- b. Hemoglobin > 8 g/dL with or without transfusions;
- c. Platelet > 100×10^9 /L;
- d. Serum creatinine $\leq 1.5 \times$ ULN, OR calculated creatinine clearance > 50 mL/min by Cockcroft-Gault formula, OR estimated glomerular filtration rate > 50 mL/min/1.73 m²

12. Patient IS permitted to be on corticosteroids if related to disease burden and MAY have symptomatic brain lesions as long as radiation or surgical intervention is not deemed to be urgently necessary.

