4.10 Guidelines for Permanent Discontinuation

- Any Grade 2 drug-related uveitis or eye pain or blurred vision that does not respond to topical therapy and does not improve to Grade 1 severity within the re-treatment period OR requires systemic treatment
- Any Grade 3 non-skin, drug-related AE lasting > 7 days, with the following exceptions for laboratory abnormalities, drug-related uveitis, pneumonitis, bronchospasm, hypersensitivity reactions, infusion reactions, and endocrinopathies:
 - Grade 3 drug-related uveitis, pneumonitis, bronchospasm, hypersensitivity reaction, or infusion reaction of any duration requires discontinuation
 - Grade 3 drug-related endocrinopathies adequately controlled with only physiologic hormone replacement do not require discontinuation
 - Grade 3 drug-related laboratory abnormalities do not require treatment discontinuation except:
 - ◆ Grade 3 drug-related thrombocytopenia > 7 days or associated with bleeding requires discontinuation
- Any drug-related liver function test (LFT) abnormality that meets the following criteria require discontinuation:
 - AST or ALT > 8 x ULN
 - Total bilirubin > 5 x ULN
 - Concurrent AST or ALT > 3 x ULN and total bilirubin > 2 x ULN
- Any Grade 4 drug-related AE or laboratory abnormality, except for the following events which do not require discontinuation:
 - Grade 4 neutropenia ≤ 7 days
 - Grade 4 lymphopenia or leukopenia
 - Isolated Grade 4 amylase or lipase abnormalities that are not associated with symptoms or clinical manifestations of pancreatitis. The Study PI should be consulted for Grade 4 amylase or lipase abnormalities.
 - Isolated Grade 4 electrolyte imbalances/abnormalities that are not associated with clinical sequelae and are corrected with supplementation/appropriate management within 72 hours of their onset

Phase I/II study of encorafenib and binimetinib with nivolumab and low dose ipilimumab in metastatic *BRAF* mutant melanoma

- Any event that leads to delay in dosing lasting > 6 weeks from the previous dose requires discontinuation, with the following exceptions:

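### Two prior-toxicity bars in the Synopsis and 3.1 are missing from the 3.3 entry list, and exclusion 2 is broader in scope than 3.1

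*Combined protocol and SAP*

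**What the plan says.** The Study Design text of the Synopsis and section 3.1 state the same prior-toxicity conditions in the same paragraph that defines who may take part. The first is that "Toxicity from prior treatment must have resolved to ≤ Grade 1". Section 3.1 adds that the history must not include "previous Grade 3–4 irAEs that required treatment discontinuous or previous Grade 2 immune-related uveitis or pneumonitis"; the Synopsis says the same.

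Section 3.3 then gives the operative list, opening with "For entry into the study, the following criteria MUST be met". It holds 16 inclusion criteria (3.3.1), 14 exclusion criteria (3.3.2) and one Group 1 criterion (3.3.3). The only item that deals directly with toxicity on earlier therapy is exclusion 2: "Previous Grade 3-4 AEs, or discontinuation of PD-1 or CTLA-4 inhibitor therapy, or BRAF/MEK inhibitor therapy".

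Inclusion 6 admits patients more than 6 months past adjuvant therapy, patients who started targeted therapy within the last 6 weeks, and patients who have had one cycle of immunotherapy.

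**The concern.** An entry condition that appears only in the design narrative is easy to miss when eligibility is confirmed against the numbered list. Here the missing conditions are safety conditions, and the population makes them relevant. The current text admits patients after one cycle of immunotherapy, and the amendment rationale expects some of them to have started it in the community, so a prior immune-related event is a real question at screening.

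The protocol itself treats these events as serious. Section 4.7 counts Grade 2 pneumonitis lasting more than 7 days despite corticosteroids as a DLT, and 4.10 makes unresponsive Grade 2 drug-related uveitis a ground for permanent discontinuation. Section 1.1.2.3 reports that an earlier combination of a BRAF inhibitor with ipilimumab was dropped for hepatic DLT before MEK inhibitors were added. Cohort 1 also gives a BRAF inhibitor with ipilimumab and no MEK inhibitor.

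The second problem is that 3.1 and exclusion 2 describe the Grade 3–4 bar differently, so the sponsor's intended scope cannot be read from the text.

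**Working it through.** No stated figure depends on this point, so the check sets the texts side by side.

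**Step 1. Conditions against the list.** Numbered criteria in 3.3: 16 + 14 + 1 = 31.

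| Condition in the Synopsis and 3.1 | In 3.3.1–3.3.3? |
|---|---|
| Prior toxicity resolved to Grade 1 or less | 0 of 31 |
| No previous Grade 3–4 irAE that required discontinuation | Only as exclusion 2, with a different scope |
| No previous Grade 2 immune-related uveitis or pneumonitis | 0 of 31 |

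**Step 2. Do neighbouring criteria close the gap?** Only in part.

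- *Patient with resolved Grade 2 immune-related pneumonitis, prior drug not stopped.* Exclusion 2 starts at Grade 3. Exclusion 5 concerns steroids or immunosuppressants within 14 days, not history. Exclusion 6 concerns autoimmune disease and permits conditions not expected to recur without an external trigger. The list does not clearly stop this patient; 3.1 does.
- *Patient with resolved Grade 2 immune-related uveitis.* The same reasoning applies. Exclusion 14 covers retinal vein occlusion and its risk factors, and retinal degenerative disease, but not uveitis.
- *Patient with an ongoing Grade 2 transaminase rise from prior treatment, no steroids.* Inclusion 11 has four items: neutrophils, hemoglobin, platelets and renal function. None is hepatic. Exclusion 2 again starts at Grade 3. The list does not stop this patient; 3.1 does.

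Exclusion 1 (contraindication to a study drug) might be used in such cases, but only at the investigator's judgement.

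**Step 3. Scope of exclusion 2.** It can be parsed in two ways: any previous Grade 3–4 AE, or Grade 3–4 AEs on PD-1, CTLA-4 or BRAF/MEK therapy. Under either, it reaches events that are not immune-related and events that did not lead to discontinuation, and it adds BRAF/MEK therapy. Section 3.1 names only immune-related events that required discontinuation. A resolved Grade 3 irAE on a prior checkpoint inhibitor, drug continued, is therefore barred by exclusion 2 on both parses, and the discontinuation qualifier in 3.1 has no effect.

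**Step 4. The word *discontinuation*.** Exclusion 2 gives no reason for it. Inclusion 6 admits patients who completed adjuvant therapy, and 3.1 says that patients who progressed more than 6 months "following completion of adjuvant therapy (either *BRAF*-MEK or PD1 Ab) will be eligible for participation in high risk disease cohort expansion". These texts conflict only if completing a planned course counts as discontinuing it.

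**The case against.** The strongest reply is that 3.1 is part of the protocol and binds. Entry then requires both 3.1 and 3.3, the stricter text governs, and there is one answer for each patient in Steps 2 and 3. Sites must also go outside 3.3 for the Group 2 definition, because inclusion 10 refers to it and 3.3.3 covers only Group 1. Registration under 4.4 requires confirmation of eligibility, and an exclusion broader than 3.1 errs towards safety.

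Most of this stands, and it limits the finding. A reader might infer that 3.1 and 3.3 contradict each other, for example that 3.1 admits the patient with a resolved Grade 3 irAE whom exclusion 2 bars. The documents do not support that: 3.1 states necessary conditions and admits nobody by silence. A reader might also infer that exclusion 2 shuts out the adjuvant-treated patients of inclusion 6. That needs *completion* to be read as *discontinuation*, which is not ordinary usage, and the Synopsis elsewhere links discontinuation with toxicity. It is an ambiguity to remove, not a conflict.

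The reply does not dispose of the omission. It relies on staff finding safety conditions in narrative text outside the list presented as mandatory, and it does not explain why 3.1 carries a qualifier that exclusion 2 makes redundant.

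**Conclusion.** The point holds as a defect of placement and scope. Two of the three prior-toxicity conditions are absent from all 31 criteria of the entry list; the third is there only in a broader and ambiguous form. Screening from that list alone could enrol patients whom the design bars on safety grounds.

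This assumes that the sponsor means the Synopsis and 3.1 conditions to apply, as their wording indicates, and that some sites will work mainly from 3.3. The number of patients affected cannot be derived from the documents and is probably small. A reader might go on to infer a distorted DLT rate or RP2R decision; nothing in the documents supports that, and no stated statistical figure changes. The correction is worth making because it is specific, relevant to safety and cheap.

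**What to change.** Add two exclusions to 3.3.2: (a) toxicity from prior treatment not resolved to Grade 1 or less; (b) previous Grade 2 or higher immune-related uveitis or pneumonitis. Adding *or higher* to (b) prevents a gap if the narrower Grade 3–4 scope is chosen: a Grade 3 event that did not lead to discontinuation would otherwise pass while a Grade 2 event is barred.

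Reword exclusion 2 as: previous Grade 3–4 AEs on, or discontinuation for toxicity of, PD-1, CTLA-4 or BRAF/MEK inhibitor therapy. Use the same scope in 3.1 and the Synopsis, unless the sponsor intends the narrower one, in which case use that in all three places.

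The sponsor may also wish to decide whether (a) should exempt endocrinopathy controlled on hormone replacement. Exclusion 6 already permits "residual hypothyroidism due to autoimmune condition only requiring hormone replacement", and 4.10 says of treatment on study that "Grade 3 drug-related endocrinopathies adequately controlled with only physiologic hormone replacement do not require discontinuation". Neither is an exception to the entry condition, so an exemption would relax it and is not part of this correction.

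The cost is an eligibility wording amendment with IRB review under 9.1.1. Sample size, schedule and analysis do not change.

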3.4 Concomitant Treatments

3.4.1 Prohibited and/or Restricted Treatments

The following medications are prohibited during the study (unless utilized to treat a drug-related AE):

- Immunosuppressive agents
- Immunosuppressive doses of systemic corticosteroids (except as permitted in brain metastasis cohort).
- Any concurrent anti-neoplastic therapy (ie, chemotherapy, hormonal therapy, immunotherapy, extensive, non-palliative radiation therapy, or standard or investigational agents for treatment of melanoma with the exception of targeted therapy initiated within the last 6 weeks, or one cycle of immunotherapy).

